PNAC was first described by Peden and colleagues [3] and has long been recognized as a major cause of morbidity and mortality in neonates and infants. [4, 5] PNAC can be associated with liver dysfunction, cirrhosis, and hepatic carcinoma. The proposed mechanisms that could explain cholestasis caused by the total parenteral nutrition are multifactorial. The major mechanisms include hemodynamic modifications within the biliary system caused by parenteral administration of nutrients, bile stasis resulting from decreased stimulation of gastrointestinal hormones in the absence of any enteral intake, direct toxic effects of TPN components, premature biliary system, and bacterial overgrowth leading to overproduction of deconjugated bile acids. Very few observational studies done earlier have looked at the association of PNAC with various nutritional components of TPN. The findings of these studies indicate that PNAC could be associated with increased duration of TPN [6, 7] with almost all infants developing PNAC by 6 weeks on TPN [8,9,10], higher intake of amino acids [11], higher intake of dextrose, intake of trace elements like aluminium [12], copper and manganese [13], and cumulative amount of intravenous lipid intake[14]. Several preventive trials have been conducted in neonates involving the use of different amounts of protein intake or the use of choleretic medications in order to prevent cholestasis. Vileisis and colleagues [11] did not find any difference in the incidence of PNAC when they compared amino acids intake of 2.3gm/kg/day vs. 3.6 gm/kg/day. Their findings were reciprocated by Clark and colleagues [15] who found no difference in the incidence of PNAC when comparing amino acids supplementation of 2.5 vs. 3.5gm/kg/day. Similarly, the use of both cholecystokinin (CCK) [16], and ursodeoxycholic acid [17] failed to prevent the development of PNAC. Majority of these preventive trials performed in neonates defined PNAC as direct bilirubin ≥ 2 mg/dL after two weeks on PN [9, 11, 21]. Because these preventive trials failed to identify any

preventive therapy, there is a need to identify alternative ways to prevent PNAC in high-risk infants.

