- k) **Primary Outcome Measures:** PNAC will be the primary outcome measure and will be defined as direct bilirubin ≥ 2 mg/dl developing within one week of the completion of 6 week randomization period in the absence of other known causes (discussed earlier). Total serum bilirubin and direct bilirubin concentration will be measured once weekly as part of the standard of care when on parenteral nutrition. The direct bilirubin is usually measured until the resolution of direct hyperbilirubinemia as part of the standard of care. If parents have consented, we will collect blood that is leftover from blood draws that are done as part of standard of care.

The blood samples will be stored in -80 degree freezer in the PI's laboratory within the Department of Neonatology for possible future research on intravenous nutrition and its effects on the liver such as identifying a more sensitive biochemical marker than direct bilirubin concentration of liver injury. Samples will be stored with a study number only and will only be linked to the data collected for the purposes of this study. Only study team members will have access to the stored blood and will be able to use the samples. Future research on stored blood after completion of this study will only be conducted by the PI on IRB approval.

- l) Secondary Outcome measures:** Secondary outcome measures will include peak direct bilirubin concentrations during hospital stay, use of choleretic medications and use of Omegavan during the hospital stay and percentage weight gain during the 6 week study period.
- m) Data Safety Monitoring:** There are several reasons why independent data safety monitoring and stopping rules were not considered for this study as described below:
 - 1) In this study, the outcome measure, direct hyperbilirubinemia $>2.0\text{mg/dL}$, is the potential side effect of interest secondary to intravenous lipid intake. As per the standard of care, the intravenous lipid intake of 1-2 gm/kg/day is routinely used in the presence of direct hyperbilirubinemia of 2 mg/dL to provide essential calories and prevent essential fatty acid deficiency. Usually, choleretic medications such as cholecystokinin are used to resolve PNAC at this point.

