 - 2) Our hypothesis is that the development of PNAC is causally related to the cumulative lipid intake, however, protein and glucose intake may modify the association between lipid intake and PNAC. In addition, sepsis and prematurity are confounding risk factors. The sample size calculated ($n=40$) to evaluate the outcome measure (or the adverse event) accounts for the variable duration of the TPN (cumulative lipid intake) and presence of confounding risk factors. Therefore, meaningful statistical analysis is not possible with an interim analysis of less than 40 subjects.
 - 3) As suggested by our observational study, a mean cumulative dose of 55gm/kg (SD 15) of intravenous lipid is required before the development of PNAC in late preterm and term

infants. Thus, it is expected that an infant on 1gm/kg/day of intravenous lipid arm will take ~ 55 days to develop PNAC. Therefore, considering the fact that TPN intake will often be less than 42 days among study subjects, not all infants in either group are expected to develop PNAC. PNAC, the study outcome, as defined for the purpose of the study, is the earliest when any medications are used to treat PNAC as per the standard of care. Severe PNAC is defined when direct bilirubin concentration is > 10 mg/dL and is very rare. The randomization of intravenous lipid intake will be stopped long before severe PNAC may be seen among enrolled subjects.

- 4) Performing interim analyses will require more stringent significance level which will increase the sample size required to perform the study. This is a pilot study performed as part of fellow's project for which 40 subjects are required for meaningful analysis of outcome (or adverse event)
- 5) This study has been designed as a block randomization with each block having 8 subjects with 1:1 assignment, so even if all enrolled infants were to develop PNAC, it will suggest that there is no difference between the two groups and there is no causal association between intravenous lipid intake and cholestasis.

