Because of reasons mentioned even if the first 20 subjects (50%) hit the direct bilirubin endpoint, interim analysis is unlikely to allow meaningful analysis of the causation between lipid intake and the outcome measure (or adverse event) as provided in the protocol. In other words, it is unlikely to reach adjusted statistical significance required for interim analyses. Thus, since the outcome measure and the adverse event are the same and the sample size required to evaluate the association (or the adverse event) controlling for other factors is 40, no interim analysis and stopping rules were considered for this pilot study. For trial management, the investigation team will track enrollment and protocol compliance and review every 3 months.

V. DATA COLLECTION: The baseline data on demographics and clinical factors (antenatal and postnatal) before randomization on each subject will be collected. Similarly, data on clinical factors will be collected during the 6 week study period or until the subject is receiving intravenous lipid as per

randomization or until the subject develops PNAC (direct bilirubin ≥ 2 mg/dl in the absence of concurrent infection).

The information on TPN components, specifically amount of lipid, protein, and glucose intake on each day will be prospectively collected using pharmacy and TPN records. Information on cumulative amount of lipid intake, cumulative amount of protein intake, and cumulative amount of glucose intake will be determined for all enrolled subjects. The additional information that will be collected is duration (days) of TPN, use of trace elements, duration (days) of NPO, type of enteral feeds (maternal breast milk vs. Formula) duration (days) of antibiotic use, onset and duration of choleric medications, sepsis defined as blood culture positivity or clinical signs and symptoms of sepsis with the use of antibiotics for > 3 days, day of life when the infant reaches an enteral intake of 120 ml/kg/day, duration (days) of mechanical ventilation, duration of CPAP, duration of oxygen supplementation, and amount of erythrocyte transfusions during the study period. However, use of choleric medications and discontinuation of trace elements from the TPN is not expected during the study period based on the unit policy as delineated earlier.

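### Section IV(m) waives trial-level safety review on grounds that mostly concern interim testing of PNAC, and its one calculation covers only the 1 g/kg arm

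*Combined protocol and SAP*

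**What the plan says.** Section IV(m) opens by stating that "There are several reasons why independent data safety monitoring and stopping rules were not considered for this study" and closes by repeating that "no interim analysis and stopping rules were considered for this pilot study". In between it gives five reasons:

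1. PNAC is both the outcome and the side effect of interest, and lipid at 1 to 2 g/kg/day is routine care even at a direct bilirubin of 2 mg/dL.
2. The sample of 40 is what the adjusted analysis needs, so an interim look would not be meaningful.
3. From the group's observational study, "a mean cumulative dose of 55gm/kg (SD 15) of intravenous lipid is required before the development of PNAC". From this: "Thus, it is expected that an infant on 1gm/kg/day of intravenous lipid arm will take ~ 55 days to develop PNAC". Parenteral nutrition will often last less than 42 days, so "not all infants in either group are expected to develop PNAC". Severe PNAC, defined as direct bilirubin above 10 mg/dL, is described as very rare, and: "The randomization of intravenous lipid intake will be stopped long before severe PNAC may be seen among enrolled subjects".
4. Interim analyses need a stricter significance level and hence more infants.
5. If every infant developed PNAC, that would point to no difference between arms.

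The only recurring review is this: "For trial management, the investigation team will track enrollment and protocol compliance and review every 3 months".

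Protection of the individual infant is set out elsewhere. Randomised lipid ends at direct bilirubin of 2 mg/dl or more (Sections IV(f), IV(g) and IX), and lipid is then at the attending neonatologist's discretion (Section IX). Bilirubin is measured weekly during parenteral nutrition (Section IV(k)). Peak direct bilirubin is a secondary outcome (Section IV(l)). Assignments are available only to the research pharmacist (Section VII(a)).

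**The concern.** The trial tests whether more lipid causes a complication that, in Section II, "has long been recognized as a major cause of morbidity and mortality in neonates and infants". The arm expected to carry more of it is the 2 g/kg arm, yet the worked time in reason 3 is for the other arm. A reader of Section IV(m) sees a time longer than the treatment period and is not told that the same figure falls well inside that period at the higher dose.

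Reason 3 also makes a forecast about severe PNAC that could turn out wrong. As written, no one is asked to look at severe cases or deaths across infants while enrolment continues. By-arm counts would first be seen at the end, when they can no longer inform whether to keep randomising.

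**Working it through.** **1. The plan's own figures.** Time to PNAC is mean cumulative dose divided by daily dose. At 1 g/kg/day this is 55 / 1 = 55 days, which agrees with reason 3. The sample size is not in question either. With 20 per group, 40% control incidence and hazard ratio 3.6, Freedman's formula with full 6-week follow-up gives 20 × [0.40 + 1 − 0.60^3.6] = 24.8 events and 80.4% power, against the stated 80.0%.

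**2. The missing arm.** At 2 g/kg/day, 55 / 2 = 27.5 days of lipid. One SD either side (40 to 70 g/kg) is 20 to 35 days. Section IV(g) starts every infant at 1 g/kg/day and gives no number of days before the increase. With k days at the starting dose, the time is k + (55 − k) / 2: 28 days for k = 1 and 31 days for k = 7 (a range of 1 to 7 days is assumed). All of these lie inside 42 days and close to the 4-week median follow-up in Section VI.

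**3. Why percentages should not be built on this.** Suppose the threshold is normal with mean 55 and SD 15, and lipid is uninterrupted. The share reaching it by day 42 is then:

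- 1 g/kg: Φ((42 − 55) / 15) = 19%
- 2 g/kg: Φ((84 − 55) / 15) = 97%

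Section VI assumes 40% at 6 weeks in the control group. If that is the 1 g/kg arm, hazard ratio 3.6 implies 1 − 0.60^3.6 = 84% in the other. The two sets disagree, the normal shape is an assumption, and both describe PNAC at 2 mg/dl rather than severe PNAC. Only the time in step 2 follows directly from the plan.

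**4. What each reason covers.**

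| Reason | Subject | Bears on counting severe events? |
|---|---|---|
| 1 | Both doses are routine care | Supports light monitoring |
| 2, 4, closing paragraph | Power and alpha of an interim PNAC comparison | No: a count tests no hypothesis and spends no alpha |
| 3 | Time to PNAC; severe PNAC forestalled | Yes, but the time is given for one arm and the forecast is not checked |
| 5 | What it would mean if all infants had PNAC | No: it concerns causation |

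**5. The individual stop, side by side.** Sections IV(f) and IV(g) end randomised lipid at direct bilirubin of 2 mg/dl or more only without sepsis. Section V ends data collection at the same level without concurrent infection. Section IX states the stop with no such condition. Under IV(f) and IV(g), an infant with sepsis and raised bilirubin could stay on assigned lipid; under IX, as worded, the infant would not. Reason 3 relies on this stop.

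**6. Number of reviews.** At about 25 eligible admissions a year (Section III), 40 infants take at least 40 / 25 = 1.6 years and 52 take 52 / 25 = 2.1 years. That is about 6 to 8 quarterly reviews, none with a safety item.

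**7. What a count would do.** The plan gives no severe rate, so the rates below are assumed, and a referral count of 2 is used only as an illustration. The chance of reaching it is 1 − (1 − p)^n − n·p·(1 − p)^(n−1):

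| True severe rate p | n = 40 | n = 52 |
|---|---|---|
| 1% | 6% | 10% |
| 2% | 19% | 28% |
| 5% | 60% | 74% |
| 10% | 92% | 97% |

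**The case against.** The waiver is deliberate and argued. Its best support is reason 1: both arms fall within doses the unit already uses, and this is a 40-infant, single-unit pilot. That stands as a case for a light mechanism, and no separate committee is asked for here.

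The individual stop is a real safeguard. It acts at one fifth of the severe threshold, with weekly measurement, so a value above 10 mg/dL would normally arise after assigned lipid had ended. A count of severe cases would then partly reflect discretionary care. This stands as a limit on interpretation. It does not remove the value of seeing counts by randomised arm, and the stop's own wording is not settled.

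Reason 3's conclusion also survives: that not every infant in either arm will develop PNAC is compatible with 27.5 days at 2 g/kg, since many infants will come off parenteral nutrition earlier. The omission makes the argument incomplete rather than false.

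A count is a coarse tool. At an assumed 5% rate, the chance of two cases among the first 20 infants is only 26%. A pooled count also does not single out an excess in one arm, which is why counts by arm are needed.

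A reader might infer that the plan leaves infants unprotected, or that nearly all infants at 2 g/kg would come to serious harm. The documents support neither. Individual stops exist, and the 97% in step 3 is a model figure for the 2 mg/dl endpoint on uninterrupted lipid. The documents contain no rate of severe cholestasis in either arm.

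**Conclusion.** The point holds at trial level. Section IV(m) sets aside all review of accumulating harm, and apart from reason 1 its reasons either concern an interim PNAC comparison and its interpretation or rest on a time worked for one arm. The omitted time is about 27.5 days, or 28 to 31 with titration. It assumes only that the plan's 55 g/kg applies equally at both doses and that lipid is continuous; interruptions would lengthen it.

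It would go too far to say that an excess of severe cholestasis at 2 g/kg is likely, or that nothing would happen if one arose: each infant's randomised lipid is meant to end first. What is missing is any check across infants that this works as reason 3 asserts.

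One caution: Section VII is lettered a, c, d in the text available, so an item on adverse-event handling may have been removed. The explicit statements in Section IV(m) stand regardless. The change is worth making because it is cheap, but the point does not undermine the primary analysis.

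**What to change.** Keep the decision to have no interim efficacy analysis, and make three changes.

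1. In reason 3, add the approximate time to PNAC for the 2 g/kg arm (about 27.5 days, or 28 to 31 allowing for the starting dose). Leave out the model-based percentages, which conflict with Section VI.
2. Reconcile the sepsis condition on the individual stop across Sections IV(f), IV(g), V and IX. Which wording applies is for the sponsor and clinicians to decide.
3. Extend the 3-monthly review to the cumulative number of infants with direct bilirubin above 10 mg/dL and the number of deaths. The research pharmacist supplies counts by arm to the IRB or another reader outside the investigation team. If a count set in advance by the sponsor is reached, the IRB is asked whether enrolment should continue.

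The count should cover every infant randomised, including any later reclassified as screen failures and replaced under Section VII(a).

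The cost is a few sentences and one added review item. Peak direct bilirubin is already collected; deaths would have to be added to the Section V data items. No alpha is spent, and no infant's dose or care is changed by the review item. The downside is a small chance of an unnecessary referral. The sponsor should calculate it for up to 52 infants under its own assumed severe rate, since the plan gives none; step 7 shows how strongly it depends on that rate.

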i) Subjects will receive glucose, protein, vitamins, and trace elements at the discretion of the attending neonatologist as per the standard of care. The unit policy regarding nutrition is to gradually increase protein intake to 3 to 4 gm/kg/day and intravenous glucose intake as tolerated to provide a caloric intake of 90 – 110 kcal/kg/day. Assuming the average intake of 120ml/kg/day of TPN, the predicted amount of caloric intake from the non-fat portion of the TPN would be ~ 90 kcal/kg/day (assuming protein intake of 3 to 4 gm/kg/day and an average dextrose concentration of 15% via the central line). The clinical team will assume an average lipid intake of 1.5gm/kg/day for each enrolled infant during the period of the study which is equivalent to a caloric intake of 13.5 ± 4.5 kcal/kg/day from lipid intake. Thus the total caloric

intake for the infants in the study would be $90 + 13.5 \pm 4.5$ Kcal/kg/day or 103.5 ± 4.5 Kcal/kg/day. If the enrolled subject does not gain weight despite reaching allowable maximum protein supplementation, there will be room for increasing caloric intake by increasing the amount of glucose intake (either by increasing dextrose concentration or increasing total fluid intake). Increasing glucose intake for weight gain is the standard of care in our NICU while limiting lipid intake in neonates at risk for cholestasis.

- j) In case of hypertriglyceridemia, the unit protocol of intravenous lipid intake will be used and the RP will be notified. According to the unit policy, the Intravenous lipid intake will be halved when the serum triglycerides level is between 250 to 350 mg/dl and would be stopped when the serum triglycerides is >350 mg/dl. Once the hypertriglyceridemia has resolved, the assigned intravenous lipid intake will be resumed as per the randomization arm. The discontinuation of trace elements and the administration of choleretic medications will be done as per the unit policy. According to the unit policy, the use of trace elements will be discontinued if direct bilirubin is ≥ 2 mg/dl. Similarly, the unit policy is to add choleretic medications when direct bilirubin level is ≥ 2 mg/dl. The care team will be requested to adhere to these unit policies during the conduct of the study.

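### Section V's limit on data collection conflicts with the windows of the four secondary outcomes and, followed literally, would truncate them

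*Combined protocol and SAP*

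**What the plan says.** Section V (Data Collection) sets the period for post-randomisation data: "data on clinical factors will be collected during the 6 week study period or until the subject is receiving intravenous lipid as per" the allocation, and then "randomization or until the subject develops PNAC". PNAC is defined there as direct bilirubin of at least 2 mg/dl without concurrent infection. The sentence joins three limits with 'or' and does not say which one governs.

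Section IV(l) gives the secondary outcomes their own windows. Three run over the hospital stay: "peak direct bilirubin concentrations during hospital stay", and "use of choleretic medications and use of Omegavan during the hospital stay". The fourth is "percentage weight gain during the 6 week study period".

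Other passages that bear on the point:

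- Section IV(j): "the unit policy is to add choleretic medications when direct bilirubin level is" 2 mg/dl or more. This is the same threshold as the primary event.
- Section V lists the start and length of choleretic treatment among the items to record. It then says that such use is not expected within the study period.
- Section IV(k): "The direct bilirubin is usually measured until the resolution of direct hyperbilirubinemia as part of the standard of care".
- Section IV(h) has weight assessed daily so that lipid can be dosed. Section IX ends randomised lipid once direct bilirubin reaches 2 mg/dl.

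**The concern.** The secondary outcomes need data from after the point at which section V, read literally, stops collecting them. Choleretics are worst placed, because they begin when collection ends. In an infant with PNAC, the highest bilirubin recorded could be simply the first value at or above 2 mg/dl. Omegavan given later would go unrecorded. Weight gain would cover whatever time passed before PNAC or before the end of randomised lipid.

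The stop depends on the primary event and on feeding progress, and the trial's own hypothesis makes the first differ by arm. Weight gain is the only growth outcome listed in a comparison of less with more lipid, so unequal follow-up matters most there. Section VII(d) gives no method for unequal follow-up in secondary outcomes.

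**Working it through.** **1. Windows side by side**

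| Outcome | Window in IV(l) | Section V taken literally | In section V's list? |
|---|---|---|---|
| Peak direct bilirubin | Hospital stay | Ends at PNAC or end of randomised lipid | Not listed; routine measurement described in IV(k) |
| Choleretic use | Hospital stay | Ends at the level that triggers the drug | Yes, start and length |
| Omegavan use | Hospital stay | Ends at PNAC or end of randomised lipid | No |
| Percentage weight gain | 6 weeks | Ends at PNAC or end of randomised lipid | No follow-up weight listed; daily weight for dosing only |

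**2. The plan's own figure.** Inputs from section VI: 20 per group, two-sided 0.05, control incidence 40% at 6 weeks, median follow-up 4 weeks, HR 3.6, power 80%.

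- Weekly control hazard, assuming it is constant: −ln(0.6)/6 = 0.0851. Other arm: 3.6 × 0.0851 = 0.3065.
- Events with 4 weeks of follow-up: 20 × (0.289 + 0.707) = 19.9.
- Schoenfeld power: Φ(√19.9 × ln 3.6 / 2 − 1.96) = Φ(0.90) = 0.815.
- The same method gives 0.808 and 0.804 for the rows 50%/3.26 and 60%/3.02.

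The stated 80% is reproduced to within 2 points, so these inputs can be used to size the stopping.

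**3. Stops caused by PNAC, no censoring.** The documents do not name the control arm; 1 g/kg is assumed.

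- By week 4: 1 − 0.6^(4/6) = 28.9%, and 1 − 0.6^(3.6 × 4/6) = 70.7%.
- By week 6: 40.0%, and 1 − 0.6^3.6 = 84.1%.
- In infants: 20 × (0.289 + 0.707) = 19.9 of 40 by week 4, and 20 × (0.400 + 0.841) = 24.8 of 40 by week 6.

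**4. Adding stops at full feeds.** Randomised lipid also ends when parenteral nutrition is no longer needed (section IV(f)). Assume that time to full feeds is exponential with a 4-week median, equal in both arms: m = ln 2 / 4 = 0.1733 per week. With PNAC hazard λ, over 6 weeks:

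- PNAC first = λ/(λ+m) × [1 − exp(−6(λ+m))]
- Feeds first = m/(λ+m) × [1 − exp(−6(λ+m))]

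| Section VI row | PNAC first, 1 g v 2 g | Feeds first | Any early stop |
|---|---|---|---|
| 40%, HR 3.6 | 26% v 60% | 53% v 34% | 79% v 94% |
| 50%, HR 3.26 | 33% v 66% | 49% v 30% | 82% v 96% |
| 60%, HR 3.02 | 40% v 71% | 46% v 27% | 86% v 98% |

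The contrast in any early stop is modest: 94/79 = 1.2. The cause differs by arm, and most infants in both arms would have no week-6 weight.

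**5. Cross-check on direction.** Section IV(m), item 3, puts the mean cumulative lipid dose before PNAC at 55 g/kg. That is 55/1 = day 55 at 1 g/kg/day and 55/2 = about day 27.5 at 2 g/kg/day, ignoring the start at 1 g/kg/day in the higher arm. The direction is the same.

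**The case against.** A reader might infer that all four secondary outcomes are cut off at the primary event. The documents do not establish that. The stopping sentence governs data on clinical factors and follows a sentence about baseline factors, so it can be read as covering covariates and exposures only. Section IV(l) gives each outcome its own window. Bilirubin is usually followed to resolution, and the length of choleretic treatment could not be recorded if collection ended when the drug began. Some stops come at full feeds, not at PNAC.

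A reader might also infer that choleretic use would be near zero in both arms. That goes too far. Section V's PNAC requires absence of concurrent infection, and the unit policy in IV(j) has no such exception, so an infected infant could receive choleretics while collection continues. Section VII(d) mentions choleretics only to argue that they come after the outcome and so are unlikely to confound. That fits a hospital-stay outcome.

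Nor do the figures support a flat statement that truncation is 2.1 to 2.4 times as common at 2 g/kg (84/40 and 71/29). HR 3.6 is a detectable effect, not a forecast. The ratio counts only PNAC stops and ignores full feeds, although section IV(m) expects parenteral nutrition often to last less than 42 days.

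These objections limit the claim but leave the conflict in place. Routine bilirubin measurement is a description of care, not a commitment to collect study data. The choleretic item sits in a list tied to the study period, in which its use is not expected. Omegavan and follow-up weight are not in the list, and the daily dosing weight loses its purpose once randomised lipid ends.

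**Conclusion.** The finding holds as an unreconciled conflict between a stated stopping rule (section V) and stated outcome windows (section IV(l)). Truncation follows only if staff apply section V literally. In that case most choleretic use would be missed, later bilirubin peaks and Omegavan use could be missed, and weight gain would be compared over unequal periods.

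On the section VI inputs, PNAC-driven stopping would be about 29% v 71% by week 4 and 40% v 84% by week 6 without censoring. With the assumed feeding pattern it would be about 26% v 60%, with any early stop at about 79% v 94%. These figures assume constant hazards, 1 g/kg as control and a true effect equal to the detectable one. The difference between arms is a design expectation, not a documented fact.

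The trial is a self-described pilot and these are secondary outcomes. The primary analysis is not affected by this point. The wording should still be corrected, because the remedy is cheap and data not abstracted could leave the secondary comparisons uninformative or biased.

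**What to change.** Reword section V so that the following holds for every randomised infant, regardless of PNAC, end of parenteral nutrition or end of randomised lipid:

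- All direct bilirubin values already measured in routine care, and all choleretic and Omegavan use, are abstracted to discharge.
- Weight is abstracted to day 42. For infants discharged earlier, use the last inpatient weight, report days of follow-up by arm, and also express weight gain per day. Some inequality of follow-up then remains, but it is visible and no longer set by the stopping rule.
- Omegavan use and follow-up weight are added to the list of items collected.

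The bilirubin item is deliberately limited to routine values. Section IV(k) describes weekly measurement during parenteral nutrition and then until raised values resolve, so infants off parenteral nutrition without PNAC may have none. The number of values per infant should be reported by arm alongside the peak.

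The cost is a change of wording and longer chart abstraction. It needs no new blood draws and no change to clinical management.
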